6.2. Preparation/Handling/Storage/Accountability

Details on storage, handling, and allowable excursions for GSK3439171A investigational product (IP), placebo, and solutions are provided in the Technical Agreement.

1. A description of the detailed methods and materials required for preparation of GSK3439171A solution or capsule and placebo are provided in the Technical Agreement.
 2. The solution and capsules will be extemporaneously prepared at the clinical site as per instructions in the Technical Agreement that will be reviewed and approved by GSK prior to use.
 3. The investigator or designee must confirm appropriate temperature conditions have been maintained during transit for all study intervention received and any discrepancies are reported and resolved before use of the study intervention.
 4. Only participants enrolled in the study may receive study intervention and only authorized site staff may supply or administer study intervention. All study interventions must be stored in a secure, environmentally controlled, and monitored (manual or automated) area in accordance with the labeled storage conditions with access limited to the investigator and authorized site staff.
 5. The investigator, institution, or the head of the medical institution (where applicable) is responsible for study intervention accountability, reconciliation, and record maintenance (i.e., receipt, reconciliation, and final disposition records).
 6. Further guidance and information for the final disposition of unused study intervention are provided in the Technical Agreement.
- Under normal conditions of handling and administration, study intervention is not expected to pose significant safety risks to site staff. Take adequate precautions to avoid direct eye or skin contact and the generation of aerosols or mists. In the case of unintentional occupational exposure notify the monitor, Medical Monitor and/or GSK study contact.
 - A Material Safety Data Sheet (MSDS)/equivalent document describing occupational hazards and recommended handling precautions either will be provided to the investigator, where this is required by local laws, or is available upon request from GSK.

Precaution will be taken to avoid direct contact with the study intervention. A MSDS describing occupational hazards and recommended handling precautions will be provided to the investigator. In the case of unintentional occupational exposure notify the monitor, Medical Monitor and/or GSK study contact.

6.3. Measures to Minimize Bias: Randomization and Blinding

6.3.1. Randomization

Study using Pre-Coded Randomization provided to site	Before treatment begins at the beginning of each part of the study, participants will be assigned a unique number (randomization number) in ascending numerical order at the study site. The randomization number encodes the participant's assignment to the respective arms of the study, according to the randomization schedule generated prior to the study by the Clinical Statistics Department at GSK. Each participant will be dispensed blinded study intervention, labeled with his/her unique randomization number throughout the study.
---	--

In Part A, approximately 9 participants in each cohort will be randomized to one of 3 treatment sequences (AAP, APA & PAA, where A represents an active dose of GSK3439171 and P represents placebo). Within each period, allocation of active (A) to placebo (P) treatment will be 2:1. Within a cohort, an increasing dose of GSK3439171A will be administered in each period as illustrated in the table below. Planned doses are provided in Section 6.6. At each dose level, sentinel dosing will be employed, such that one subject is dosed with placebo and another with active dose of GSK3439171A and followed for 48 hr prior to the rest of the subjects receiving their randomized treatment.

Cohort	Sequence	Period 1	Period 2	Period 3
Cohort 1	AAP	D1	D2	Placebo
	APA	D1	Placebo	D3
	PAA	Placebo	D2	D3
Cohort 2	AAP	D4	D5	Placebo
	APA	D4	Placebo	D6
	PAA	Placebo	D5	D6
Cohort 3	AAP	D7	D8	Placebo
	APA	D7	Placebo	D9
	PAA	Placebo	D8	D9

In each cohort of Part B, approximately 12 participants will be randomized to receive either GSK3439171A or placebo in a parallel design using a 3:1 allocation ratio. Participants will receive a single dose followed by a 72 hr assessment period and then will receive daily repeat doses until the end of the study.

Dose Cohort	Regimen
B1	R1 mg GSK3439171A or placebo QD or BID
B2 ¹	R2 mg GSK3439171A or placebo QD or BID
B3 ¹	R3 mg GSK3439171A or placebo QD or BID

1. Dose levels for Cohorts will be determined based on real-time analysis of the safety, tolerability, PK, and preliminary PD data from Part A and therefore may be adjusted from predicted dose levels listed.

QD – Once daily

BID- Twice daily

Regimen	Period 1	Period 2
X	GSK3439171A ¹ administered in the fasted state	GSK3439171A ¹ administered after a high fat meal
Y	GSK3439171A ¹ administered after a high fat meal	GSK3439171A ¹ administered in the fasted state

- ¹ Dose to be determined based on data from Part A of the study

In Part C, approximately 12 participants will be randomized 1:1 to receive GSK3439171A in one of two treatment sequences (Fed then Fasted or Fasted then Fed).

Participants who do not complete the study may be replaced at the discretion of the investigator in consultation with the sponsor.

6.3.2. Blinding

Blind Break (Envelopes)	
A sealed envelope that contains the study intervention assignment for each participant will be provided to the investigator. The sealed envelope will be retained by the investigator (or representative) in a secured area.
 
In case of an emergency, the investigator has the sole responsibility for determining if unblinding of a participant's treatment assignment is warranted. Participant safety must always be the first consideration in making such a determination. If the investigator decides that unblinding is warranted, the investigator should make every effort to contact GSK prior to unblinding a participant's treatment assignment unless this could delay emergency treatment of the participant. If a participant's treatment assignment is unblinded GSK must be notified within 24 hours after breaking the blind. The date and reason that the blind was broken must be recorded in the source documentation and electronic case report form (eCRF), as applicable.
 
Once the study is complete, all envelopes (sealed and opened) must be inventoried and returned to GSK.

--------------------------------	--

A participant may continue in the study if that participant's intervention assignment is unblinded.

Participants will be randomized to receive study intervention. Investigators and all site staff with the exception of the pharmacy staff will remain blinded to each participant's assigned study intervention throughout the course of the study. In order to maintain this blind, unblinded site pharmacy staff will be responsible for the dispensation of all study intervention and will endeavour to ensure that there are no differences in time taken to dispense following randomization. The site staff will instruct the participant to avoid discussing the taste, dosing frequency, or packaging of the study intervention with the investigator.

Unblinded monitors and, in the event of a Quality Assurance audit, the auditor(s), will be allowed access to un-blinded study intervention records at the site to verify that randomization/dispensing has been done accurately.

A participant will be withdrawn if the participant's treatment code is unblinded by the investigator or treating physician. The primary reason for discontinuation (the event or condition which led to the unblinding) will be recorded in the eCRF.

GSK's Global Clinical Safety and Pharmacovigilance (GCSP) staff may unblind the intervention assignment for any participant with an SAE. If the SAE requires that an expedited regulatory report be sent to one or more regulatory agencies, a copy of the report, identifying the participant's intervention assignment, may be sent to investigators in accordance with local regulations and/or GSK policy.

Members of the GSK clinical study team will be unblinded for dose-escalation data reviews. This team may include but is not limited to the study statistician, programmers, physician project leader, Muscle Metabolism Discovery Performance Group leader, Clinical Investigation Lead, Operations Science Lead, Data Quality Lead, pharmacokineticist, DMPK analyst, safety review team, and other decision makers. At the time of the data reviews, access to the randomization will be restricted to randomization numbers that have been assigned to participants in the cohort(s) under review.

6.4. Study Intervention Compliance

- When the individual dose for a participant is prepared from a bulk supply, the preparation of the dose will be confirmed by a second member of the study site staff.
- When participants are dosed at the site, they will receive study intervention directly from the investigator or designee, under medical supervision. The date and time of each dose administered in the clinic will be recorded in the source documents. The dose of study intervention and study participant identification will be confirmed at the time of dosing by a member of the study site staff other than the person administering the study intervention. Study site personnel will examine each participant's mouth to ensure that the study intervention was ingested.

6.5. Concomitant Therapy

Any medication or vaccine (including over-the-counter or prescription medicines, vitamins, and/or herbal supplements) that the participant is receiving at the time of enrollment or receives during the study must be recorded along with:

- reason for use
- dates of administration including start and end dates
- dosage information including dose and frequency

The Medical Monitor should be contacted if there are any questions regarding concomitant or prior therapy.

Participants must abstain from taking prescription or nonprescription drugs, including vitamins and dietary or herbal supplements (including St. John's Wort) within 10 days (or 14 days if the drug is a potential enzyme inducer) or 5 half-lives (whichever is longer) before the start of study intervention until completion of the follow-up visit, unless, in the opinion of the investigator and sponsor, the medication will not interfere with the study.

Due to potential effects on GSK3439171A's related pathways, neither aspirin nor NSAIDS of any kind are permitted for use from 10 days prior to the start of the study through the follow-up visit. Acetaminophen or another medication selected by the investigator and the Medical monitor may be administered as prescribed (acetaminophen not to exceed 4,000 mg/24 hr per current guidelines) by attending study staff if simple analgesia is required during the study. Local anaesthesia will be used for muscle biopsy procedures. Other concomitant medication may be considered on a case-by-case basis by the investigator in consultation with the Medical Monitor.

6.6. Dose Modification

This protocol allows some alteration from the currently outlined dosing schedule, number of participants, and number of cohorts needed based on the emerging safety, PK, and PD data, but the maximum daily dose and/or (predicted) maximum/cumulative exposure will not exceed 3000 mg (based on GRA limit), 57.8 $\mu\text{g}\cdot\text{h}/\text{ml}$ for single dose AUC exposure limit in Part A (based on liver effects in dog at 600 mg/kg male dog), or 11.0 $\mu\text{g}\cdot\text{h}/\text{ml}$ for repeat dose AUC exposure limit in Part B (based on mean NOAEL exposure for liver effects in 20 mg/kg female 6-week dog study) respectively. The AUC stopping exposure limit of 11 $\mu\text{g}\cdot\text{hr}/\text{mL}$ s for the repeat dose phase were set by the rat adrenal toxicity is below (0.24 times) the lowest effect exposure for rat adrenal toxicity

Information regarding dose escalation review processes is detailed in the Dose Escalation Plan. Briefly, the GSK medical monitor, in joint discussion with the participating investigator(s) (to remain blinded during the study), will be responsible for making dose escalation decisions. Prior to the dose escalation decision, the GSK clinical team, which includes but is not limited to, the medical monitor, clinical scientists, safety physician and/or representative, and clinical pharmacokineticist, will review critical safety data defined in Section 8.2, Section 8.3, and in the Dose Escalation Plan. This includes review of all adverse events including non-dose-limiting toxicities, laboratory assessments and

other defined safety evaluations, as well as PK and PD data when appropriate. Quality control of critical safety data will also be described in the Dose Escalation Plan, which includes ongoing study monitoring visits, Sponsor review of the clinical database, and confirmation by site investigators and/or delegates that the data are accurate and complete.

The dose-escalation decision and rationale for each cohort will be discussed with the investigator(s) during teleconference(s) and documented in writing, with copies maintained at each study site and in the study master file.

The decision to proceed to the next higher dose level will be made by the clinical study team in consultation with the investigator(s) based on the evaluation of data from at least 4 participants (Part A) or 6 participants (Part B) who received active treatment at the preceding lower dose. Such decisions will be based on the safety and tolerability, as well as PK data observed at the lower dose level and the predicted exposure at the next dose level. Some doses may be deleted and intermediate and/or higher/lower doses may be added as appropriate during the study as the results of safety/tolerability, PK, and PD assessments become available.

The details on the dose escalation committee can be found in Section [9.5.1](#)

6.6.1. Dose Escalation in Part A

In Part A, the decision to proceed to the next dose level of GSK3439171A will be made based on evaluation of the safety, tolerability and preliminary PK data as outlined in Section [4.1](#).

The primary preclinical exposure parameter that will guide dose escalation in Part A is based on single dose exposure limit in the male dog at 600 mg/kg/day (AUC(0-24h)) at steady state – 57.8 µg·h/mL described in Section [4.3](#). Assuming time-invariance, the Day 1 AUC(0-inf) observed in each of the human participants in this study at each single dose will be compared to the above value in order to determine the magnitude of dose escalation.

The following algorithm will be used for dose escalation in Part A:

1. For each dose group, the human mean AUC (0-inf) on Day 1 will be calculated as percentage of the male dog at 600 mg/kg/day of AUC(0-24) steady-state (57.8 µg·h/mL). Example dose escalation based on single dose exposure limit exposures is provided below. Some of the above doses may be deleted and intermediate and/or higher doses may be added as appropriate during the study as the results of safety/tolerability and PK assessments become available. The next dose level can then be determined as described in the example table below:

Table 2 Mean simulated exposures at SD of GSK3439171A compared to single dose exposure limit set by male dog at 600 mg/kg/day exposures levels

Dose (mg)	Mean Simulated AUC(0-inf) ($\mu\text{g}\cdot\text{h}/\text{mL}$)	Fold cover from 600 mg/kg male dog AUC(0-24) ¹	Mean Simulated Cmax ($\mu\text{g}/\text{mL}$)	Fold cover from 600 mg/kg male dog Cmax ¹	Simulated % H-PGDS inhibition maintained for 24 hours ²
5	0.10	578	0.01	1000	10
20	0.39	158	0.05	200	20
50	0.99	58	0.12	83	40
100	1.97	29	0.24	42	60
300	5.91	10	0.72	14	80
500 ^a	9.85	6	1.20	8	85

¹ Compared to systemic exposure at 600 mg/kg/day in male dog steady-state AUC(0-24) and Cmax values (57.8 $\mu\text{g}\cdot\text{h}/\text{mL}$ and 10 $\mu\text{g}/\text{mL}$, respectively)

² Represents the simulated mean GSK343171A concentrations maintained at different H-PGDS inhibition levels over 24 hours

Fewer or more dose levels may be explored based on emerging data from Part A.

- The highest dose in Part A will not exceed 3000 mg based on GRA limits.
- The highest predicted mean Day 1 AUC (0-inf) in Part A will not exceed 57.8 $\mu\text{g}\cdot\text{h}/\text{ml}$.

Dosing in Part C (food effect) can be initiated after the exposures achieved with at least two dose levels administered in a fasted state are calculated. The dose levels chosen for Part C will ensure an adequate safety margin to allow for an increased exposure of GSK3439171A in the presence of food.

6.6.2. Dose escalation in Part B

Part B can be initiated after the safety and PK data of at least four dose levels from Part A are evaluated. The decision to initiate Part B will be made by the clinical study team in conjunction with the investigator.

Dose selection in Part B will be based on the safety/tolerability and PK data from Part A. The following rules will guide dose selection in Part B:

- The starting daily dose in Part B will be selected such that its predicted exposure (mean AUC(0-24) and Cmax) on the last day of dosing is no higher than the Day 1 exposure of a dose that has been found to be well tolerated and had no safety signals of concern in Part A. As the highest exposure with repeat dosing is expected on the last day of dosing (as a result of accumulation), this approach would select a daily dose which provides blood concentrations that, at any time during the period of dosing, are no higher than the ones already found to be well tolerated and had no safety signals of concern in Part A. The expected exposure on the last day of dosing

will be predicted based on the PK parameters for GSK3439171A established in Part A.

2. Subsequent doses in Part B may be selected using the criteria described above for the starting dose. Alternatively, a dose may also be selected even if it does not meet these criteria provided it is no more than 4-fold higher than a previous dose that has been found to be well tolerated and had no safety signals of concern upon repeat dosing in Part B.
3. The highest daily dose in Part B will not exceed the highest single dose that has been found to be well tolerated and had no safety signals of concern in Part A.
4. The highest predicted mean AUC(0-24) on the last day of dosing in Part B will not exceed 11.0 $\mu\text{g}\cdot\text{h}/\text{ml}$ (based on mean NOAEL exposure for liver effects in 20 mg/kg female 6-week dog study and is below (0.24 times) the lowest effect exposure for rat adrenal toxicity).

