1. PROTOCOL SUMMARY

1.1. Synopsis

Protocol Title: A Three-Part FTIH Study to Evaluate Safety, Tolerability, Pharmacokinetics and Pharmacodynamics of Single and Repeat Oral Doses of GSK3439171A, in a Randomized, Double-Blind (sponsor unblinded), Placebo-Controlled, Dose Escalation study and to Evaluate the Effect of Food on a Single Oral Dose of GSK3439171A in Healthy Adult Participants

Short Title: FTIH Study to evaluate the safety, pharmacokinetics, and pharmacodynamics of single and repeat doses of GSK3439171A in healthy participants; food effect

Rationale: The FTIH study with GSK3439171A will evaluate the safety of GSK3439171A in healthy participants in order to avoid confounding factors due to the disease or concomitant drugs in patients. The study design is based on pre-clinical findings for GSK3439171A, contributing to the frequency, type and duration of safety assessment and monitoring during treatment periods in each cohort.

The single dose assessments in Part A will be conducted to determine safety, tolerability, pharmacokinetics (PK), and pharmacodynamics (PD) of the study intervention in individuals before progressing to doses explored further in other parts of the study and will allow for any adjustments needed based on emerging safety, tolerability, and PK information. Part A will also serve to identify a dose for use in examining the effect of food on GSK3439171A exposure in Part C.

In Part B, a single dose safety, tolerability and PK will be collected followed by progression of these participants to the repeat dose portion of the study. The up to 14-day dosing was chosen as it is thought to provide sufficient safety and tolerability data to bridge to longer duration studies. The dosing period can be adjusted depending on PK and PD data collected in Part A of the study. Part B will involve more detailed PK/PD/metabolite assessments to better understand the impact of GSK3439171A on target engagement and metabolism in humans. In addition, based on the PK obtained in Part A, an additional cohort will be enrolled to study higher exposures of GSK3439171A for a shorter duration of time.

Objectives and Endpoints:

Objective	Endpoint
Primary	

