Potential effect on endocrine system (adrenal gland)	In juvenile rats, recoverable, dose responsive findings were noted in the adrenal gland (cortical hypertrophy of the zona fasciculata) with associated increased adrenal weights, pale discoloration and/or enlargement in males given ≥ 100 mg/kg/day and females given ≥ 10 mg/kg/day. As the findings may be considered potentially adverse for repeat clinical dosing, the no adverse effect level (NOEL) for adrenal gland histologic	The AUC stopping exposure limit of 11 $\mu\text{g}\cdot\text{hr}/\text{mL}$ for the repeat dose phase is below (0.24 times) the lowest effect exposure for rat adrenal toxicity and participants will be monitored at times indicated in the SoA for changes in the following levels:

Potential Risk of Clinical Significance	Summary of Data/Rationale for Risk	Mitigation Strategy
	effects was 10 mg/kg/day in male and female rats, with associated AUC (0-t) of 3.94 µg.h/mL. The lowest individual AUC at lowest effected dose level (LOEL) of 100 mg/kg/day for male juvenile rat adrenal effects is 46 µg.h/mL.	adrenocorticotrophic hormone (ACTH), cortisol luteinizing hormone (LH), follicle stimulating hormone (FSH), thyroid stimulating hormone (TSH) total testosterone dihydrotestosterone (DHT) thyroxine (T4) triiodothyronine (T3)
Potential effect on female reproductive tissues	In female juvenile rats, recoverable, dose responsive microscopic findings were also noted in the ovary (vacuolation of interstitial cells) and mammary gland (lobuloalveolar hypertrophy/hyperplasia) at ≥100 mg/kg/day; and pituitary (increased mitoses of cells in the pars distalis) at 600 mg/kg/day.	All women will be excluded from this study.
The nonclinical toxicology and efficacy studies were conducted using non-micronized material, while	The rat and dog toxicity studies with non-micronized material attained AUC and Cmax exposures substantially over the NOAEL to effectively characterize the nonclinical safety of GSK3439171. Additionally, the	Conservative assumptions were used for the minimum anticipated biological effect level (MABEL) simulations and the predictions for the first dose are expected to be well

Potential Risk of Clinical Significance	Summary of Data/Rationale for Risk	Mitigation Strategy

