Participants will report to the Clinical Research Unit on Day -2 and will remain in the unit for the duration of Part B. Participants will randomly be assigned to receive a single dose (or a BID dose depending on data obtained in Part A) of GSK3439171A or placebo (approximately 9 study intervention: 3 placebo). Plasma and urine PK, PD, and biomarker samples (including a pre-dose muscle biopsy) will be collected for up to 72 hr after initial dosing. After completion of assessments at 72 hr (Day 4), participants will begin a repeat dosing regimen consisting of one dose (or a BID dose depending on data obtained in Part A) per day for up to 14 days. This time period is based on a predicted half-life of GSK3439171A of 6.1 hours (with a range of 4-22 hours) calculated from preclinical data and is designed to allow GSK3439171A to reach steady state during the dosing period. The actual repeat dose duration can be altered based on PK data in Part A of the study. For example, if the predicted half-life is confirmed from Part A of the study then the duration of dosing in Part B will be much shorter to achieve steady-state than planned currently. Dosing duration in Part B and follow-up will be shortened appropriately based on emerging PK data from Part A. Participants will be discharged on the morning of Day 13 (3 days post last dose during the 7 day repeat dose period) or Day 20 (3 days post-last dose during the 14 day repeat dose period) following completion of study assessments, including a post-dose muscle biopsy. Safety, tolerability and PK data review for a minimum of 6 participants receiving active treatment will be carried out upon completion of assessments on Day 13 or 20 (72 hours post-last dose) before initiation of dosing in the next cohort. The dose of GSK3439171A may be adjusted (lower or higher) based on data from Part A and for cohorts going forward based upon the safety, tolerability, PK, and preliminary PD data from the previous cohort.

All participants will return to the clinical unit for a follow-up visit approximately 14 days following the administration of the last dose of study medication.

Part C: Food Effect

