4.2. Scientific Rationale for Study Design

The FTIH study with GSK3439171A will evaluate the safety of GSK3439171A in healthy participants in order to avoid confounding factors due to the disease or concomitant drugs in patients. The study design is based on pre-clinical findings for GSK3439171A, contributing to the frequency, type and duration of safety assessment and monitoring during treatment periods in each cohort.

The single dose assessments in Part A will be conducted to determine safety, tolerability, PK, and PD of the study intervention in individuals before progressing to doses explored further in other parts of the study. The sequential design of the single dose components will allow for dose escalation to occur approximately every two weeks with a 7-day period of washout. This approach allows for any adjustments needed based on emerging safety, tolerability, and PK information. The crossover design within each cohort in Part A is preferred as it allows for each participant to serve as their own control for the assessment of safety and provides PK assessment in the same individual at two different dose levels, reducing the influence of inter-individual variability.

In Part B, a single dose safety, tolerability and PK will be collected followed by progression of these participants to the repeat dose portion of the study. The 7 or 14-day dosing was chosen as it is thought to provide sufficient safety and tolerability data to bridge to longer duration studies. The dosing period can be adjusted depending on PK and PD data collected in Part A of the study.

Prostaglandin species, particularly prostaglandin D2, are virtually undetectable in the blood or plasma of unchallenged and/or otherwise healthy human subjects. However, skeletal muscle contains high levels of prostanoids in the basal state, and our preclinical data reveal significant dose-dependent reductions in prostaglandin D2 levels in skeletal muscle following administration of H-PGDS inhibitors [GSK3439171A Investigator's Brochure]. Therefore, muscle biopsies will be performed both pre- and post-study intervention in Part B to assess the effect of GSK3439171A on prostanoid levels *in situ* in a tissue of potential clinical interest.

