Results of other nonclinical studies suggest that GSK3439171 does not present a genotoxic risk to humans. Additionally, there were no safety pharmacology findings of clinical concern at oral dog doses up to 1500 mg/kg. There were no changes considered related to GSK3439171 administration in the evaluation of spermatogenesis in either species. Thus, the nonclinical data support the conduct of clinical studies in men up to 6 weeks duration up to the mean systemic exposure at the NOEL for adrenal gland histologic effects in the rat study (AUC: 3.94 $\mu\text{g}\cdot\text{h}/\text{mL}$) with appropriate monitoring in place, and for a shorter duration of 7 days up to the dog liver NOAEL exposure (AUC: 11.0 $\mu\text{g}\cdot\text{h}/\text{mL}$).

Based on in vivo efficacy studies and mechanism of the H-PGDS pathway, the efficacy target was to maintain GSK3439171A concentrations above the IC_{50} . A 10% inhibition of the H-PGDS enzyme (IC_{10}) was considered as the minimal anticipated biological effect level (MABEL). The IC_{50} and IC_{10} were calculated from the H-PGDS recombinant enzyme inhibition assay and compared with in vivo studies (dystrophin deficient (mdx) and WT eccentric damage mouse models).

GSK3439171A in vitro inhibition was evaluated using a recombinant human H-PGDS enzyme assay. The data was fitted using an E_{max} model and the IC_{50} was 7.77 ng/mL and

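### The Part B mean-exposure cap of 11.0 µg·h/mL has no duration attached, although Section 4.3 supports that exposure for 7 days only and 3.94 µg·h/mL for longer dosing

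*Protocol*

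**What the plan says.** Protocol Section 4.3 ties supported exposure to duration. It supports "clinical studies in men up to 6 weeks duration up to the mean systemic exposure at the NOEL for adrenal gland histologic effects" (rat AUC 3.94 µg·h/mL). The higher exposure is supported only "for a shorter duration of 7 days up to the dog liver NOAEL exposure" (11.0 µg·h/mL).

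The rules that govern dosing carry one number only:

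- Section 6.6.2, rule 4: "The highest predicted mean AUC(0-24) on the last day of dosing in Part B will not exceed 11.0" µg·h/mL.
- Section 6.6 gives 11.0 "for repeat dose AUC exposure limit in Part B (based on mean NOAEL exposure for liver effects" in the 6-week female dog study).
- Section 2.3.1 says that the limit of 11 "for the repeat dose phase is below (0.24 times) the lowest effect exposure for rat adrenal toxicity".
- Section 7.1.6.2 sets the same ceiling on the predicted Part B mean.

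None of these names a duration. Part B nevertheless keeps both durations. Section 4.1 describes one dose (or a twice-daily dose "depending on data obtained in Part A) per day for up to 14 days", and Section 4.2 says "The 7 or 14-day dosing was chosen as it is thought to provide sufficient safety and tolerability data". The synopsis (1.1) explains where the higher exposure was meant to apply: "an additional cohort will be enrolled to study higher exposures of GSK3439171A for a shorter duration of time".

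**The concern.** Rule 4 and Section 7.1.6.2 are the mean-exposure ceilings on escalation in the repeat-dose part. Section 6.6 allows the dosing schedule, the number of participants and the number of cohorts to change on emerging data, within these exposure limits. If the limit is followed as written, a 14-day cohort could be planned at a predicted mean of 11.0 µg·h/mL, an exposure that the protocol's own toxicology argument supports for 7 days only.

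The lower value exists because of adrenal findings in juvenile rats, which Section 2.3.1 treats as potentially adverse for repeat clinical dosing. The participants are healthy volunteers who gain no benefit, so the written ceiling should match its justification.

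**Working it through.** **Inputs.** Section 4.3: 3.94 (rat adrenal NOEL, up to 6 weeks), 11.0 (dog liver NOAEL, 7 days) and 46 µg·h/mL (lowest individual AUC at the rat adrenal effect dose). Sections 4.3.3 and 4.3.4: 70 kg, clearance 5.7 to 19.5 mL/min/kg, bioavailability 39% to 100%. Section 6.6.1: Part A mean cap 57.8 µg·h/mL; Table 2 gives a simulated 9.85 µg·h/mL at 500 mg. SAP 5.1: listed Part A doses up to 180 mg and Part B doses of 5, 11 and 40 mg. SAP 13.4.1: half-life about 13 h.

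**1. The plan's own figures.** 11.0/46 = 0.239, which reproduces the stated 0.24. Dose = AUC × clearance × 70 × 60/1000 ÷ F. For 11.0 this gives 11.0 × 5.7 × 4.2 ÷ 1 = 263 mg and 11.0 × 19.5 × 4.2 ÷ 0.39 = 2310 mg, as in Section 4.3.4.

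**2. The gap.** 11.0/3.94 = 2.79. The excess is 11.0 − 3.94 = 7.06 µg·h/mL, and the supported value is 3.94/11.0 = 36% of the written cap. The dose range predicted to reach 3.94 is 94 to 827 mg, against 263 to 2310 mg for 11.0.

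**3. Does assessing the last day of dosing separate the durations?** No. At a 13 h half-life, 7 days is 168/13 = 12.9 half-lives, or 99.99% of steady state. The same daily dose gives practically the same last-day AUC after 7 or 14 days.

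**4. Do rules 1 to 3 of Section 6.6.2 hold a 14-day cohort below 3.94?**

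- *Rule 1* ties predicted exposure to a tolerated Part A exposure. Part A may go to a mean of 57.8, and 57.8/3.94 = 14.7, so the protection depends on how high Part A actually went.
- *Rule 2* allows a 4-fold dose step, which is larger than 2.79. With linear PK, a step from any tolerated cohort with a mean above 3.94/4 = 0.985 can pass 3.94, and a step from 11.0/4 = 2.75 reaches 11.0.
- *Rule 3* caps the daily dose at the highest well-tolerated Part A dose. With linear, time-invariant PK this also bounds daily AUC at the single-dose AUC(0-inf). On the Table 2 slope (9.85/500 = 0.0197 per mg), 180 mg gives 3.55, just under 3.94. At the protocol's expected top dose of 500 mg it gives 9.85, well over.

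The margin at 180 mg is thin: 3.94/3.55 = 1.11, so exposure 11% above the slope would cross it. The entry for Amendment 2 in Section 10.8 records that observed PK differed from the preclinical predictions, and the documents give no observed AUCs.

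**5. The listed cohorts.** The footnote to SAP Table 3 identifies Part B cohort 3 as the reduced-duration cohort, so 40 mg is the 7-day dose and 5 and 11 mg are the 14-day doses. On the same preclinical slope, 5 and 11 mg give 0.10 and 0.22 µg·h/mL (0.20 and 0.43 if given twice daily).

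**The case against.** The best defence is that the intent is already on the page. Section 4.3 restricts 11.0 to 7 days, the synopsis reserves higher exposures for a shorter cohort, and the summary of changes describes the raised limits in Sections 6.6 and 7.1 as being for 7-day dosing. SAP 3.1 shows Part A and Part B cohorts 1 and 2 complete before the decision on a higher dose for cohort 3. A further 14-day cohort would still need safety and PK review of at least 6 participants on active treatment. The Dose Escalation Plan, a separate document that is not available here, may carry the distinction.

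There is also toxicological comfort. The rat adrenal findings were recoverable. The value 11.0 comes from a 6-week dog study and is about a quarter of the lowest adrenal effect exposure. Adult male rats showed no adrenal effect in a preliminary 7-day study at a far higher exposure (AUC 1130 µg·h/mL in blood). Hormones are monitored in Part B.

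Most of this stands, and it limits the consequence. It does not supply the missing limit. Case-by-case review needs a number to work to, and the number written is 11.0. The dog study addresses the liver rather than the adrenal gland, the adult rat data cover 7 days only, and Section 4.3 still set 3.94 for longer dosing. The argument that rules 1 and 3 already bind at 180 mg is plausible, but it rests on a preclinical slope that the trial's own PK did not follow.

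**Conclusion.** The protocol is wrong as written on this point. For repeat dosing beyond 7 days, the mean-exposure cap in Sections 2.3.1, 6.6, 6.6.2 rule 4 and 7.1.6.2 is 2.79 times the mean that Section 4.3 supports, and 3.94 appears in no operating rule in the protocol. The ratio needs no modelling assumption. The statements about rules 2 and 3 assume linear PK, and rule 3 also assumes time-invariance. The practical effect is limited to an added or higher 14-day cohort, which Sections 1.1 and 6.6 permit.

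Three stronger readings are tempting, and the documents do not support them:

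- *That a listed cohort exceeds the supported exposure.* None is shown to do so.
- *That rules 1 to 3 certainly leave the gap open at the doses studied.* The documents show only that they do not guarantee closing it.
- *That the individual stop at 11.0 in Section 7.1.4 is contradicted too.* Section 4.3 does quote one individual animal value (46), but the human exposures that it supports for repeat dosing are stated as means.

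The SAP 5.1 note on additional dose levels is a display convention and should not be read as authorising further cohorts.

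**What to change.** In Sections 2.3.1, 6.6, 6.6.2 rule 4 and 7.1.6.2, limit 11.0 µg·h/mL to repeat dosing of up to 7 days, and state 3.94 µg·h/mL as the cap on predicted mean AUC(0-24) for longer dosing. Check that the Dose Escalation Plan says the same.

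Leave Section 7.1.4 to the sponsor's safety team rather than copying 3.94 into it. Assume log-normal AUC with a CV of 30% (the between-subject variability in the Section 4.3 simulations) and a cohort mean at the cap. An individual stop at 3.94 would then remove about 44% of participants (41% to 46% for CVs of 50% to 20%).

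The cost is wording in four sections, IEC/IRB approval of the amendment, and a lower ceiling for any cohort dosed beyond 7 days. It needs no new data, participants or assessments, and the 7-day cohort is unaffected.
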